10.2 Secondary study parameter(s)

Analysis of Pharmacokinetic Endpoints

MAb TB31F pharmacokinetics will be analyzed using standard non-compartmental methods using the Phoenix WinNonlin software package. The time-concentration and dosing data from all subjects who received mAb TB31F will be used to establish the half-life ($t_{1/2}$), area under the curve (AUC $0\text{--}\infty$), drug clearance (CL), and Volume of Distribution (Vd). Results will be reported as geometric means and geometric coefficients of variation for all dose groups.

SMFA will be performed to determine TRA of mAb TB31F. Differences will be assessed by comparing mean values between the groups or time points using either a two-tailed student's t-test (if comparing two groups) or a one-way ANOVA (if comparing more than two groups) or non-parametric equivalents. Paired tests will be used if pre-intervention values are compared with post-intervention values, unpaired if comparisons are made between groups. For discrete variables (e.g. the number of positive assays), the chi-squared test or Fisher's exact test will be used (two-tailed).

The relationship between plasma mAb TB31F concentrations and transmission reducing activity in SMFA will be assessed using standard empirical pk-pd models using Graphpad Prism v8.[23]

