2.2 Study Objectives

Primary objective:

- To assess the reactogenicity and safety after a single dose of mAb TB31F in terms of rates of solicited local AEs through 7 days post-administration, solicited general AEs through 28 days post- mAb administration, clinically significant hematological and biochemical laboratory abnormalities through 28 days post-mAb administration, unsolicited AEs through end of study (day 84), and serious adverse events (SAEs) through end of study.

Secondary objectives:

- To describe the serum pharmacokinetics (pK) of mAb TB31F at each dose level in healthy subjects.
- To assess the pharmacodynamics of mAb TB31F assessed as functional activity of serum in a standard membrane feeding assay at each dose level.

Exploratory objectives:

- To describe the anti-TB31F antibody response (anti-idiotypic) in terms of seropositivity rates and geometric mean titers (GMTs).
- To develop an integrated population pharmacokinetic-pharmacodynamic model for TB31F.

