4.4 Sample size calculation

TB31F is a first in human observational safety trial in healthy volunteers, designed to identify safety concerns associated with TB31F administration at different dosages. A total of twenty-five healthy adults (males and females) aged 18 – 35 will be divided over five groups. Each group will include five subjects. The study's original sample size of n=20 (four intravenous groups of n=5), was calculated to have a 90% chance of observing at least 1 event if the true rate of such an event is 10.87% or more; and there is a 90% chance of observing no events if the true rate is 0.52% or less. The 5th (subcutaneous) was subsequently pragmatically chosen to have the same size. Sample size for each group is appropriate for mAb administration Phase 1 trials based on similar trial designs for HIV, CMV, and anthrax monoclonal antibody prophylactic studies [13-15]. This is a small Phase 1 study; therefore, it is largely descriptive and is intended to provide primarily safety data of 4 escalating intravenous doses of mAb TB31F and one subcutaneous dose of mAb TB31F. Comparative statistics will be performed but will have low power to detect anything other than very large differences between the groups. 5 reserve subjects will be recruited (1 reserve subject per group).

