## Statistical Principles

### Confidence intervals and P values

Confidence intervals and P values are specified in protocol section 10 and will be based on 0.05 as significance level. Adjustments for multiple comparisons will be implemented where appropriate. Where applicable, normally distributed continuous outcomes will be presented as mean with 95% CI or standard deviations. Continuous outcomes that are not normally distributed will be transformed using a suitable transformation before reporting 95% CIs. Where a suitable transformation cannot be found, medians will be presented with interquartile ranges. For discrete (or count) data we will find interquartile ranges. Binary data will be presented as counts and proportions.

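### Applied within one dose level of five subjects, the paired non-parametric option for pre- versus post-dose SMFA comparisons cannot reach p<0.05 with exact p-values, whatever the effect

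*Protocol*

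**What the plan says.** Protocol 2.2 makes the pharmacodynamic aim a secondary objective: the "functional activity of serum in a standard membrane feeding assay at each dose level". On group size, Protocol 4.4 says "Each group will include five subjects". The footnotes to the schedule in Protocol 8.3.18 plan SMFA before dosing, at end of infusion and on days 7, 28, 56 and 84.

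Protocol 10.2 compares mean SMFA values between groups or time points "using either a two-tailed student's t-test (if comparing two groups") or by "a one-way ANOVA (if comparing more than two groups) or non-parametric equivalents". It adds: "Paired tests will be used if pre-intervention values are compared with post-intervention values, unpaired if comparisons are made between groups".

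The SAP (Confidence intervals and P values) refers back to Protocol section 10 and says that intervals and p-values "will be based on 0.05 as significance level", with multiplicity adjustment where appropriate.

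Three things are not stated in either document: which non-parametric test is meant, whether its p-value is exact or approximate, and what triggers the move away from the t-test. Protocol section 10 had promised that the SAP would set out a strategy for unmet test assumptions. The SAP's only rule of this kind (transform, otherwise medians) concerns reporting, not testing.

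The SAP's own TRA analyses (Efficacy outcome analyses) take another route: a GLM estimate for each participant and time point against pooled naive control serum, optional percentages of subjects above 50%, 80% and 90% TRA or with significant TRA, and mixed-effects concentration–TRA models.

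**The concern.** For two paired time points, the usual non-parametric equivalents of the paired t-test are the Wilcoxon signed-rank test and the sign test. Both work from the signs of the within-subject differences. With very few pairs there are too few sign patterns for any result to be rare enough to count as significant. An analyst who took this option dose by dose would report no significant change even if all five subjects went from no activity to complete blocking.

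What is at stake is how the secondary pharmacodynamic result at each dose level is read. Identical data could be called significant or not according to which permitted test is run and which software default applies, and no rule governs either choice.

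**Working it through.** **The plan's own figure.** The only sample-size statement (Protocol 4.4) is for safety events in 20 subjects. It attaches 90% probability to seeing one or more events at a rate of 10.87%, and the same probability to seeing none at 0.52%.
- At least one event: 1 − (1 − 0.1087)^20 = 0.900.
- No event: (1 − 0.0052)^20 = 0.901.

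Both reproduce. There is no corresponding figure for the SMFA comparisons.

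**Inputs.** Five pairs per dose level (Protocol 4.4); two-tailed testing and pairing (Protocol 10.2); level 0.05 (SAP). Applying the test separately in each dose level is an inference from the wording of the objective in Protocol 2.2.

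**Smallest exact p-value.** Under the null hypothesis each of the 2^n sign patterns is equally likely. The most extreme result (all differences in one direction) and its mirror image give a minimum two-sided p of 2/2^n.

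| Pairs | Minimum exact two-sided p |
|---|---|
| 4 | 2/16 = 0.125 |
| 5 | 2/32 = 0.0625 |
| 6 | 2/64 = 0.031 |

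Enumerating all 32 patterns confirms 0.0625 at n=5, with or without ties. Four pairs is a realistic case: the SAP does not impute missing data, and Protocol 8.3.5 accepts that SMFA samples may be lost in subjects with suspected or confirmed SARS-CoV-2 infection. A multiplicity adjustment could only lower the threshold further.

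**Dependence on settings.** Take five untied differences, all in one direction. The rank sum is W = 15, with mean 5×6/4 = 7.5 and variance 5×6×11/24 = 13.75.
- Exact: p = 0.0625 (also R's default on untied data).
- Normal approximation: z = 7.5/√13.75 = 2.02, p = 0.043.
- With continuity correction: z = 7.0/√13.75 = 1.89, p = 0.059.
- If all five differences are identical, R cannot compute its exact p, warns about ties and returns 0.037. The exact permutation p is still 0.0625.

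**The t-test on the same kind of data.** Assume, for illustration, a post-dose TRA of 100% in all five subjects.
- Pre-dose −20, −10, 0, 10, 20: mean difference 100, SD 15.8, t = 100/(15.8/√5) = 14.1 on 4 df, p = 0.0001.
- Pre-dose −60, −30, 0, 30, 60: SD 47.4, t = 4.71, p = 0.009.

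The exact signed-rank p is 0.0625 in both.

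**Tests that are not blocked.** The unpaired rank-sum test, 5 versus 5, has a minimum p of 2/252 = 0.008. Friedman's test across the six time points can reach about 0.0001 (chi-square approximation). A signed-rank test over 20 subjects has a minimum of about 2×10⁻⁶.

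**Behaviour of a count model at complete blocking.** This matters for the remedy. Assume 5 subjects × 20 mosquitoes, a pre-dose mean of 15 oocysts and all post-dose counts zero, in a log-link count GLM without a random effect. The coefficient runs off to −27.4 with a standard error above 13,000, so the Wald p is 0.998. The likelihood-ratio statistic on data of this kind is in the hundreds (about 755 in one run). A log-scale count model is therefore usable here only with likelihood-based inference.

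**The case against.** The strongest reply is that little rests on this test. Protocol 10.2 lists the t-test first, and it detects near-complete blocking easily: with post-dose TRA fixed at 100% and an assumed pre-dose log-ratio SD of 0.2 to 0.6, simulated power was about 89% to 100%. Section 10.2 names neither the signed-rank nor the sign test and does not say that pre/post tests are run within each group of five. TRA is defined against control serum, and the SAP estimates it per sample by GLM. Protocol 4.4 warns of low power, and no escalation or stopping rule uses these p-values.

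Most of this stands and limits the point to one permitted option. Two things remain. The SAP still sends the reader to Protocol section 10 for p-values, so the paired sentence has not been withdrawn. And the low-power caveat in 4.4 implies that very large differences between groups could still be detected, whereas this test cannot detect even the largest possible within-group change.

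A reader might also infer that the fallback would be used precisely where activity is strongest, because TRA piles up at 100%. The documents do not support that. No rule sends ceiling data to the fallback, and a paired test works on differences: if every post-dose value is 100%, the difference is 100 minus the pre-dose value, and the ceiling adds no non-normality. In simulated groups of five under the same assumptions, a Shapiro–Wilk test rejected normality in only about 6% to 12%.

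**Conclusion.** The point holds in a limited form. One option that Protocol 10.2 allows, the paired rank or sign test, has zero power with exact two-sided p-values if it is used within a single dose level: the minimum p is 0.0625 with five pairs and 0.125 with four. An approximate p-value can fall on either side of 0.05 on the same data.

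This assumes that the fallback is chosen, that it is applied per dose level, and that exact two-sided p-values are used. The arithmetic needs no assumption about effect size or variability.

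A reader might conclude that the plan will declare complete blocking in all five subjects non-significant. That goes too far, because the paired t-test and the GLM estimates are both available and neither has this limit. The consequence is moderate: a secondary endpoint in a mainly descriptive trial. Because the option can never answer the per-dose question, there is no reason to keep it.

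**What to change.** In Protocol 10.2 and the SAP:

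1. Remove the paired rank or sign test within a single dose group.
2. For each dose level and time point, report TRA with a 95% CI from the GLM already planned in the SAP (Efficacy outcome analyses). Use likelihood-ratio or profile-likelihood inference, not Wald, so that all-zero oocyst counts are handled. Since that GLM is now specified per participant, the dose-level version should say how it allows for several mosquitoes per subject.
3. Report the number of the five subjects with TRA of at least 80%, with an exact CI. The SAP already offers the percentage as an option; the interval is new.
4. If a pre/post p-value per dose level is wanted, specify the paired t-test. An exact signed-rank or sign-flip test stratified by group may be added as an overall test only, because pooling over groups does not answer the per-dose question.

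The cost is a few lines of wording and slightly more modelling. The per-group intervals will be wide: 5 of 5 subjects has an exact 95% lower limit of 0.025^(1/5) = 48%.

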10.3 Other study parameters

Analysis of Immunogenicity Endpoints

Analysis of immunogenicity for emergence of anti-idiotypic antibodies against the study product, mAb TB31F will be measured in terms of seropositivity rates and geometric mean titers (GMTs) with exact 95% CI in samples collected at the same time points as samples drawn for pK measurements.

Non-linear mixed effects modeling

The obtained pharmacokinetic pharmacodynamic data will be further analyzed by means of non-linear mixed effects modeling according to best practice [23, 24] by the Radboud Applied Pharmacometrics group. Using an exploratory approach, we will fit single and multicompartmental methods to the obtained pharmacokinetic data and investigate both linear and non-linear elimination and disposition. Thereafter, we will investigate whether the pharmacokinetics relate with inhibition of plasmodium transmission, as assessed with the membrane feeding assay, using standard empirical pk-pd models. The developed model will be used for exploratory *in silico* analysis of the pharmacokinetics and pharmacodynamics in various dosing regimens by performing Monte Carlo simulations.

10.4 Interim analysis

There are no statistical criteria for study termination in this clinical trial. Safety and reactogenicity data will be evaluated after each mAb TB31F administration before proceeding to the next group. A summary report of AEs will be provided to the SMC after all four groups have completed follow-up.

10.5 Accounting for Missing, Unused, and Spurious Data

The SAP will be followed even if data are missing. For the safety analysis, data from all subjects who received a dose of mAb TB31F in the study will be included. Subjects with missing data will not be imputed. Subjects who miss an appointment date will not be removed from the study. Rather, their appointment and laboratory values will be recorded by appropriate missing value notation in the clinical database. Non-analyzable data will be documented in the deviations.

11. ETHICAL CONSIDERATIONS

11.1 Regulation statement

This study will be conducted in accordance with the latest Fortaleza revision of the Declaration of Helsinki (2013), the Medical research Involving Human Subjects act (WMO), the ICH Good Clinical Practice, and local regulatory requirements. The investigators are responsible for obtaining all relevant ethical approvals of the protocol and any subsequent amendments in compliance with local law before the start of the study.

11.2 Recruitment and consent

As soon as the study is approved by the accredited METC and competent authority, healthy subjects will be recruited to participate in the study. Advertisements will be placed in prominent places on university campuses and other public places as well as on the intranet of the University and social media. Furthermore, a Facebook page (link: <http://www.facebook.com/malariavacinn>) showing the advertisement text will be used to inform people about the trial. This brief advertisement will indicate a telephone number to call and an e-mail address for contact to request further information. It will furthermore indicate a website (www.malariavacinn.nl) which contains a form. This short questionnaire will be completed using the online form. When seemingly suitable subjects contact investigators via e-mail, telephone or the online form, they will be invited to an information meeting during which the study will be explained to them by the study investigator. Directly after the meeting they will be provided with documents to review at home (the information sheet, the informed consent form, the application form and the insurance text). During and after the meeting there will be time for questions. After this free discussion with the investigator, and any follow-up discussion if necessary, the volunteer will be given sufficient time to consider participation.

Subjects who are interested in participating will be asked to fill in the application form and will be invited to come for a screening visit. Eligible subjects may only be included in the study after providing written, METC- approved informed consent. Informed consent must be obtained before conducting any study-specific procedures (i.e. all of the procedures described in the protocol, including screening procedures). The process of obtaining informed consent should be documented in the subject source documents. During the screening visit, the questionnaire answers will be discussed and inclusion and exclusion criteria will be checked. In addition, a letter for the general practitioner will be signed and sent after screening. Again, the investigator will answer any questions the volunteer has. The possibility of withdrawal from the study, at any time, without penalty and without any declaration of the reason will be pointed out to the subjects. The investigators will be responsible for providing adequate verbal and written information regarding the objectives and procedures of the study, the potential risks involved and the obligations of the subjects. Subjects will be informed that they will not gain health benefits from this study. Trainees or other students who might be dependent on the investigators or the study group will not be included in the study.

11.3 Benefits and risks assessment, group relatedness

The compelling need for new methods of malaria interventions need to be balanced with the potential risks and discomforts for the subjects. Risks for subjects are related to administration with mAb TB31F. There are no direct benefits to participation in the trial for subjects. Subjects will be advised to take regular malaria chemoprophylaxis when travelling to malaria endemic areas in the future. All partners in this proposal are aware of and follow the relevant national and international rules and regulations as they pertain to access to material of human origin and clinical research. International agreements such as the Declaration of Helsinki will be observed and respected.

11.4 Ethical aspects concerning the use of human subjects

Testing in human subjects remains the only reliable and convincing way to obtain information on the immunological responses that are important for protection against malaria. Of course, the compelling need for a malaria vaccine and treatments needs to be balanced with the potential risks and discomforts of the subjects. Explorative studies looking for new and complementary candidate malaria interventions are of paramount importance with the potential of large-scale application in endemic countries.

The study will be undertaken in accordance with Good Clinical Practices (GCP), according to the standards defined in the EEC directive 91/507/EEC, and in the Directive on Good Clinical Practice in Clinical Trials (ICH GCP, 75/318/EEC, January 1997) and under the principles of the Declaration of Helsinki; ethical permission will be sought from an accredited METC in the Netherlands.

11.5 Compensation for injury

The sponsor/investigator has a liability insurance which is in accordance with article 7 of the WMO. The sponsor (also) has an insurance which is in accordance with the legal requirements in

the Netherlands (Article 7 WMO). This insurance provides cover for damage to research subjects through injury or death caused by the study.

1. € 650.000,-- (i.e. six hundred and fifty thousand euro) for death or injury for each subject who participates in the research;
2. € 5.000.000,-- (i.e. five million euro) for death or injury for all subjects who participate in the research;
3. € 7.500.000,-- (i.e. seven million five hundred thousand euro) for the total damage incurred by the organisation for all damage disclosed by scientific research for the sponsor as 'verrichter' in the meaning of said Act in each year of insurance coverage.

The insurance applies to the damage that becomes apparent during the study or within 4 years after the end of the study.

11.6 Compensation

Enrolled subjects will receive up 850,- euros (groups 1-4) or 900,- euros (group 5) in compensation for their time and for the inconveniences of taking part in this study. These amounts are based on predefined criteria:

- Screening and inclusion: 100,- euros
- Inconvenience of blood tests and/or visits: 25,- euros per blood sampling
- 1 day admission to hospital: 125,- euros
- MAb TB31F administration: 300,- euros
- Compensation length of study: 20,- euros per month (3 months)

Travel expenses will not be additionally reimbursed, and compensation will not be provided to subjects who are not enrolled i.e. screen failures. Eligible subjects who are enrolled at the inclusion visit as back-ups, will be compensated 50,- Euros for each inclusion visit. If a subject withdraws from the study prior to completion, they will receive reimbursement proportional to number of visits they attended. These compensation amounts are reasonable and in line with Dutch common practice. In case of unexpected medical complications, there will be access to state-of-the-art medical treatment with full costs covered by the insurance of Radboudumc.

12. ADMINISTRATIVE ASPECTS, MONITORING AND PUBLICATION

12.1 Handling and storage of data and documents

A data management plan will be developed prior to start of study describing data management activities from project set-up through data lock and transfer. Designated trial staff will enter the data required by the protocol into the electronic CRF (eCRF). All data should be recorded, handled and stored in a way that allows its accurate reporting, interpretation and verification. An external monitor will review the data entered into the eCRFs by investigational staff for completeness and accuracy and will instruct the site personnel to make any required corrections or additions. Queries are made during each monitoring visit. Designated investigator site staff are required to respond to the queries and confirm or correct the data. Medical history/current medical conditions and adverse events will be coded using the ICD-10 terminology.

12.1.1 Source data

Prior to the start of the trial it will be determined which documents completed by the investigative team will be considered source documents. Only authorized study staff and representatives of the sponsor and authorized regulatory agencies may have direct access to source documents containing study data. Data for this study will include biographical, medical history, clinical (signs, symptoms, prescription and non-prescription medical treatments), safety and laboratory data. All information in original records and certified copies of original records, clinical findings, or observations will be considered source data for this study. The memory aids, produced by the study subjects are also considered source data. They will be kept as source documents in the investigator's clinical file. Since all subjects will be healthy, there is no medical file for the study subjects, with exception of the medical file in case of adverse events/reactions resulting in a medical consultation or hospitalization. In this case the medical file will also be considered as the source data.

All data collected by the investigators is reported in electronic case report forms. All information on eCRFs must be traceable to the source documents in the subject's file. As with all parts of the eCRF, there is an audit trail in place to register every data entry. The investigator will also keep the original informed consent form signed by the subject (a signed copy is given to the subject). The site PIs/institutions will maintain the information collected from CRFs and in the eCRFs and all source documents that support the data collected from each subject in a secure area and treated as confidential material. Documents and data pertaining to the study will be kept in a locked cabinet under the responsibility of the investigator. Periodic monitoring visits will ensure that the data is safe and stored in this secure place and that only those authorized study staff have access to the data.

Data and biological samples from this study will be stored for 20 years for research related to malaria immunology and transmission dynamics. New immunological or molecular tests may become available in the future that could strengthen or validate this research or help find important new findings. Should material be used for research not related to malaria, permission from the METC

must be granted.

